9.4.3. Other Analyses

9.4.3.1. Pharmacokinetic Analyses

All PK analyses will be performed on the PK Population and will be reported by cohort and study intervention within each cohort (ie, ALXN1820 or placebo).

The individual serum concentration data from participants who receive ALXN1820 SC or ALXN1820 IV with actual sampling dates and times will be used to derive the PK parameters by noncompartmental analyses methods.

The following PK parameters as appropriate and data permitting will be derived:

Parameters	Dosing Regimen	Definitions
C_{max}	SD, MD	Maximum observed serum concentration
t_{max}	SD, MD	Time to maximum observed serum concentration
[name]	Area under the serum concentration versus time curve from time 0 to the last quantifiable concentration
AUC_{tau}	MD	Area under the concentration-time curve during the dosing interval
$AUC_{0-\infty}$	SD	Area under the concentration-time curve from time 0 (dosing) to time infinity
$t_{1/2}$	SD, MD	Terminal elimination half-life
λ_z	SD, MD	Terminal-phase elimination rate constant
CL or CL/F	SD	Total body clearance or apparent clearance
V_d or V_d/F	SD	Volume of distribution or apparent volume of distribution
F	SD	Absolute bioavailability
R_{ac}	MD	Accumulation ratio

Abbreviations: SD = single-dose; MD = multiple-dose

The absolute bioavailability for the ALXN1820 SC cohorts will be defined by the ratio of the geometric means for the $AUC_{0-\infty}$ (area under the concentration-time curve from time 0 [dosing] to time infinity) parameter for the ALXN1820 SC cohort over the ALXN1820 IV cohort. For the absolute bioavailability estimates, a 95% CI for each of the ratio of the geometric means will be provided.

Additional details will be provided in the SAP.

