All ALXN1820 dose levels/dosing regimens can be adjusted in accordance with safety, tolerability, and PK/PD data collected up to the decision-making time point (see [Table 19](#) for dose escalation rules). As used here, the term "dosing regimen" includes (1) the dose level administered, (2) the number of doses administered each day, (3) the interval between individual doses, and (4) the duration of dosing, i.e., the total number of doses administered. Accordingly, these can be adjusted individually or in combination.

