A single dose of 450 mg will be administered by the IV route (Cohort 5) to healthy participants after completion of the 450 mg SC cohort (Cohort 4) to estimate the absolute bioavailability of ALXN1820 following SC administration (Table 16). Given the high SC bioavailability in the cynomolgus monkey, the SC bioavailability in humans is expected to be close to 100%. Hence, the exposure of ALXN1820 following a 450 mg IV dose is anticipated to be similar to that following a 450 mg SC dose. Dosing of Cohort 5 will start based on the Investigator's review of all available safety data through Day 8 (168 hours) for Cohort 4. However, in case there are safety findings in previous cohorts, an SRC review will be conducted and dosing for Cohort 5 may be started at the planned dose of 450 mg IV or at a lower dose than 450 mg IV.

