6.1. Study Intervention Administered

The study drug composition and doses to be administered in this study are presented in [Table 18](#). Placebo will be commercially available normal saline for SC administration, and 5% dextrose or glucose for IV administration. Placebo will be sourced from the site.

Table 18: Dose Reference Chart for Study ALXN1820-HV-101

Characteristics	ALXN1820 SC	ALXN1820 IV
Dosage formulation	ALXN1820 is formulated at pH 5.4 and each vial contains 300 mg of ALXN1820 in 20 mM sodium acetate, 250 mM sucrose, and 0.05% polysorbate-80. The concentration is 150 mg/mL.	ALXN1820 is formulated at pH 5.4 and each vial contains 300 mg of ALXN1820 in 20 mM sodium acetate, 250 mM sucrose, and 0.05% polysorbate-80. The concentration is 150 mg/mL.
Unit dose strength(s)/dosage level(s)	12.5 mg, 50 mg, 150 mg, 300 mg, 450 mg, 1200 mg, and a dose that will not exceed 2250 mg	450 mg
Route of administration	SC	IV
Dosing instructions	The SC doses will be administered as a manual SC push (for doses \leq 300 mg) or as a SC infusion via a syringe pump (for doses $>$ 300 mg).	ALXN1820 IV will be administered as an IV infusion
Packaging and labeling	Each vial will be packaged into a kit. There will be 1 vial per kit. Both vials and kits will be labeled according to the protocol and local regulatory requirements.	Each vial will be packaged into a kit. There will be 1 vial per kit. Both vials and kits will be labeled according to the protocol and local regulatory requirements.
Manufacturer	Alexion	Alexion

Abbreviations: IV = intravenous; SC = subcutaneous.

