9.2. Serum PK Endpoint

The following PK parameters will be derived from the serum concentrations of ALXN1820:

For the single dose cohorts 1-7, PK parameters will be derived on Day 1.

For the multiple dose cohort 8, PK parameters will be derived on Day 1 and 29.

For the multiple dose cohorts 8 and 9, PK parameters will also be derived on Day 8, 15 and 22 (when possible using limited sampling schedule up to 24h*).

For the multiple dose cohort 10, PK parameters will be derived on Day 1, 8 (when possible using limited sampling schedule up to 24h*) and 15.

* Only selected PK parameters might be derived due to limited sampling up to 24 h such as C_{max} , t_{max} , and AUC_{0-24} etc.

Refer to Section 1.3 of the Protocol for the full sample schedule.

Parameters	Dosing	Definition
C_{max}	SD, MD	Maximum observed serum concentration
t_{max}	SD, MD	Time to maximum observed serum concentration
[name]	Area under the serum concentration versus time curve from time 0 to the last quantifiable concentration
AUC_{tau}	MD	Area under the concentration-time curve during the dosing interval
$AUC_{0-\infty}$	SD, MD	Area under the concentration-time curve from time 0 (dosing) to time infinity
$t_{1/2}$	SD, MD	Terminal elimination half-life
λ_z	SD, MD	Terminal-phase elimination rate constant
CL or CL/F	SD, MD	Total body clearance or apparent clearance
V_d or V_d/F	SD, MD	Volume of distribution or apparent volume of distribution
F	SD	Absolute bioavailability
R_{ac}	MD	Accumulation Ratio

Abbreviations: MD = Multiple-dose; SD = Single dose

This document is confidential.

Note: tau is the dosing interval for steady-state data, *i.e.*, the time between doses (tau = 1 week).

The absolute bioavailability for the ALXN1820 SC cohorts will be defined by the ratio of the geometric means for the AUC_{0-∞} parameter for the ALXN1820 SC cohort over the ALXN1820 IV cohort. For the absolute bioavailability estimates, a 95% CI for each of the ratio of the geometric means will be provided.

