9.5. Planned Statistical Models for PK Parameters and Concentrations

The primary PK analysis will be based on the PK Set.

For the cohort 4 versus cohort 5 evaluation of the absolute bioavailability, the PK parameters (C_{max} , AUC_t , and AUC_{∞}) will be evaluated using an ANOVA statistical model with cohort, treatment, and sequence as the fixed effects, and participant-participant (sequence) as a random effect, using the natural logarithms of the data. Confidence intervals (CI, 90%) will be constructed for the least squares geometric mean ratio (GMR) for the cohort 4 versus cohort 5 for all 3 parameters using the natural log-transformed data. The GMRs and associated 90% confidence limits will be exponentiated back to the original scale.

The within-participant CV for the C_{max} , AUC_t , and AUC_{∞} will be estimated using the mean squared error from the ANOVA.

In addition, the geometric means and the associated 95% CIs of C_{max} , AUC_t , and AUC_{∞} will be reported for each treatment.

The evaluation of relative bioavailability, will be done for cohort 9 versus cohort 8 (for a comparison of non-Japanese versus Japanese descent).

All secondary analyses will be based on the PK Set.

Dose-proportionality will be assessed across all single dose (SD) cohorts (Cohort 1 (12.5 mg), Cohort 2 (50 mg), Cohort 3 (150 mg), Cohort 4 (450 mg), Cohort 6 (1200 mg) and Cohort 7 (\leq 2250 mg) ALXN1820) graphically and by using a power model (Smith, 2000; Newlands, 2006; EMA, 2010).

The following dose-normalized PK parameters will be assessed for dose proportionality: C_{max_n} , AUC_{t_n} and AUC_{∞_n} . The log (PK parameters) will be included as a response variable and log (dose) will be included as a fixed effect in the power model.

The form of the model is as follows:

PK Parameter = $e_{\alpha} \times \text{Dose}^{\beta} \times e_{\epsilon}$, where $\text{Dose} \geq 0$, and e_{ϵ} represents the associated error. Thus, perfect dose proportionality is met when $\beta=1$ (ignoring error). This becomes a linear relationship following a natural-log transformation, to which a linear regression will be fit by ordinary least squares (OLS):

$\ln(\text{PK Parameter}) = \alpha + \beta \times \ln(\text{Dose}) + \epsilon$, where $\text{Dose} > 0$, and ϵ represents the associated error.

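### Absolute bioavailability is defined with no dose term: sound for Cohort 4 versus Cohort 5 at the planned 450 mg, but wrong by the dose ratio if the IV dose is reduced or the definition is applied to other SC cohorts

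*Protocol*

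**What the plan says.** Estimating the absolute bioavailability of SC ALXN1820 is a secondary objective. Three places specify the analysis.

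- **Protocol 9.4.3.1:** "The absolute bioavailability for the ALXN1820 SC cohorts will be defined by the ratio of the geometric means for the" AUC to infinity, SC over IV. No dose appears. Further detail is left to the SAP.
- **SAP 9.2:** the same definition, followed by "For the absolute bioavailability estimates, a 95% CI for each of the ratio of the geometric means will be provided".
- **SAP 9.5:** "For the cohort 4 versus cohort 5 evaluation of the absolute bioavailability, the PK parameters" Cmax, AUCt and AUC to infinity are log-transformed and modelled, with a 90% interval for the geometric mean ratio. They are not dose-normalised. Dose-normalised versions of all three are in the SAP glossary, but their only stated use is elsewhere in 9.5: "The following dose-normalized PK parameters will be assessed for dose proportionality".

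On dose, Protocol 6.1 lists the SC levels as "12.5 mg, 50 mg, 150 mg, 300 mg, 450 mg, 1200 mg, and a dose that will not exceed 2250 mg"; the IV level is 450 mg. Protocol 4.3 adds that after safety findings and committee review "dosing for Cohort 5 may be started at the planned dose of 450 mg IV or at a lower dose than 450 mg IV". Tables 3, 15 and 19 carry the same allowance. Section 4.1 is broader: "All ALXN1820 dose levels/dosing regimens can be adjusted in accordance with safety, tolerability, and PK/PD data". No section says that F will be corrected for dose if the SC and IV doses differ. SAP 9.6 and SAP 14 record no departure from the protocol's analyses.

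**The concern.** A ratio of AUCs measures bioavailability only when the two doses are equal. There is one IV cohort, so the definition's plural SC cohorts and its interval for each ratio point to several SC cohorts being compared with it, and only Cohort 4 is planned at the IV dose. Even the Cohort 4 versus Cohort 5 comparison loses its equal doses if the permitted reduction in Cohort 5 is used.

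In either case the reported F would mix absorption with the dose ratio. The confidence interval would give no warning. When everyone in a cohort receives the same dose, the missing term moves the estimate and both limits by the same factor and leaves the interval just as narrow on the log scale.

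**Working it through.** The documents give no estimate, target or precision for F, so there is no figure to reproduce. Protocol 4.3 says only that "the SC bioavailability in humans is expected to be close to 100" per cent.

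**Inputs.** Planned single SC doses of 12.5, 50, 150, 450 and 1200 mg (Cohorts 1 to 4 and 6) and a planned IV dose of 450 mg (Cohort 5), from Protocol Table 14. A lower IV dose is allowed but no value is given.

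**Formula.** Let R be the ratio as defined and F the true bioavailability, with GM for geometric mean:

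- R = GM(AUC_SC) / GM(AUC_IV)
- F = [GM(AUC_SC) / Dose_SC] / [GM(AUC_IV) / Dose_IV]
- hence R = F × Dose_SC / Dose_IV

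This takes clearance to be the same at both doses.

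**Cohort 4 versus Cohort 5 as planned.** 450 / 450 = 1.00, so there is no error.

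**Cohort 4 versus a reduced Cohort 5.** The IV doses below are assumed, for arithmetic only.

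| Assumed IV dose (mg) | 450 / IV dose | R if F = 70% (assumed) |
|---|---|---|
| 400 | 1.125 | 78.75% |
| 300 | 1.5 | 105% |
| 225 | 2.0 | 140% |
| 150 | 3.0 | 210% |

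At 300 mg, a true 70% would look like the near-complete absorption that the protocol expects.

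**Literal use of the plural definition against 450 mg IV.**

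| SC dose (mg) | SC dose / 450 |
|---|---|
| 12.5 | 0.028 |
| 50 | 0.111 |
| 150 | 0.333 |
| 450 | 1.00 |
| 1200 | 2.67 |

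With true F = 100%, these factors are also the values of F that would be reported, from 2.8% to 267%.

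**Why the dose actually given matters.** Protocol 10.6 allows an infusion to be interrupted or stopped with PK sampling continuing, and SAP 8.7 compares actual with expected dose. Suppose one of six IV participants received half the dose and was kept in the analysis. The IV geometric mean would be multiplied by 0.5^(1/6) = 0.891, and R by 1 / 0.891 = 1.12.

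**Is dose normalisation enough for the other cohorts?** Predicted SC AUC over 0 to 168 h per mg, from Protocol Table 16:

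- 503 / 12.5 = 40.2
- 1685 / 50 = 33.7
- 4414 / 150 = 29.4
- 12579 / 450 = 28.0
- 32984 / 1200 = 27.5

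The sponsor's own model therefore predicts that exposure is not proportional to dose. Away from 450 mg, a dose-normalised ratio would still mix bioavailability with non-linear disposition.

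**The case against.** The best defence is that the SAP already settles the comparison. The protocol defers detail to it, SAP 9.5 names Cohort 4 versus Cohort 5, and both are planned at 450 mg. Protocol 4.3 describes the IV cohort in the same way. A reader might infer from the plural definition that the study will report F from 2.8% to 267% across SC cohorts. The documents do not support that as the planned result: those values arise only if SAP 9.5 is ignored. No factor should be attached to 2250 mg either, since it is only the ceiling for an optional cohort whose dose is not set.

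This defence stands for the planned doses but does not close the gap. SAP 9.2 repeats the plural definition and promises 95% intervals for ratios, whereas SAP 9.5 gives a 90% interval for one pair. No narrowing of the protocol's definition is recorded, so the analyst has two specifications.

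A second defence is that dose-corrected F can be recovered. SAP 9.4 derives clearance as dose over AUC to infinity, so IV clearance divided by SC apparent clearance gives it. That is correct, but no such ratio or interval is planned and the formal estimate would still be the uncorrected one.

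Third, a reduced IV dose is conditional on safety findings and would be known before analysis. That limits the likelihood of the problem. It does not supply a rule.

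Two further inferences fail. Table 16 exposures cannot be put into the definition to predict F: they cover 168 hours, while the definition uses AUC to infinity and the expected half-life at the highest SC dose is about 24 days. Nor does Cohort 5 exist only for this objective. It also provides IV safety data, feeds the interim modelling for Cohorts 7 and 10, and must be reviewed before Cohorts 6, 8 and 9 proceed.

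**Conclusion.** The point holds in limited form. The written definition lacks a dose term in both documents, and the SAP 9.5 model does not supply one. For Cohort 4 versus Cohort 5 at exactly 450 mg each, the estimate is unaffected. If Cohort 5 is dosed lower, or Cohort 4 is changed, the estimate is wrong by SC dose over IV dose: 1.5 at an assumed 300 mg IV, and 1.125 to 3.0 over the assumed range of 400 to 150 mg. If the definition were applied literally to the other planned single-dose SC cohorts, the factors would run from 0.028 to 2.67.

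The factors rest on equal clearance at the two doses and, unless stated otherwise, on every participant in a cohort receiving the same dose. The lower IV doses are assumptions. F is a descriptive secondary estimate with no hypothesis attached, so this is a specification error to correct before analysis and not a flaw in the design.

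**What to change.** 1. In Protocol 9.4.3.1, SAP 9.2 and SAP 9.5, define F as the ratio of geometric means, SC over IV, of dose-normalised AUC to infinity (AUCinf_n in the SAP glossary), dividing each participant's AUC by the dose actually given. In the log-scale model this means subtracting ln(dose) from each response. Use the existing dose-normalised Cmax and AUCt for the accompanying comparisons.
2. Align the plural definition with SAP 9.5 by naming Cohort 4 versus Cohort 5 as the estimate of F. State one confidence level, since 95% and 90% now both appear.
3. If ratios for other SC cohorts are shown, dose-normalise them and label them supportive, because predicted AUC per mg is not constant. Apply the same caution to the main estimate if the Cohort 4 and Cohort 5 doses end up different.
4. If the protocol text is left as it is, record the change in SAP 14.

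The cost is a wording change in three sections and the reuse of variables already defined. No new data are needed, and the result is identical if every participant in both cohorts receives exactly 450 mg.

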9.4.3.2. Pharmacodynamic Analyses

All PD analyses will be performed on the PD Population and will be reported by cohort and study intervention within each cohort (ie, ALXN1820 or placebo).

The PD effects of all ALXN1820 SC and ALXN1820 IV doses administered will be evaluated by assessing changes in serum total and free properdin concentrations and CAP activity using the Weislab AP assay. In addition, an exploratory assessment of CCP activity and other measures of properdin activity over time may be considered as deemed appropriate.

Biomarker assays may be conducted as an exploratory analysis on collected samples.

9.4.3.3. Immunogenicity Analysis

For assessment of immunogenicity, the incidence of confirmed positive ADAs will be summarized. Additionally, following confirmation of positive ADAs, samples will be assessed for ADA titer and presence of neutralizing antibodies (if possible).

9.4.3.4. Interim Analyses

Interim assessments will be performed as follows:

1. An assessment of all available PK/PD and immunogenicity data will be performed when all participants in Cohorts 4 and 5 reach Day 29. These data will be used to project the exposure and duration of properdin and CAP activity inhibition (not to exceed 70 days) at the highest single dose planned in the study (Cohort 7) and the highest multiple dose in the study (Cohort 10).
2. CAP activity will be continuously analyzed and will be used to estimate the time of CAP activity returning to baseline for each individual participant based on PK/PD modeling.

Refer to a separate PK/PD analysis plan for further details on the interim assessments.

Further assessments of available data may be performed to inform Phase 2 study design in patients. Details of this analysis will be presented in the SAP.

No formal interim analysis for futility is planned.

9.5. Safety Review Committee (SRC)

An SRC, consisting of Investigators from participating sites, Safety physician, Medical Monitor, Study Statistician, and Clinical Pharmacologist, will evaluate the study data at prespecified time points for participant safety and make recommendations on dose escalation, dose modification, or termination of the study. In the event a significant safety issue is identified, an ad hoc SRC meeting will be convened within 24 hours following its identification (see SRC charter for description of membership, schedule of meetings, data required for each safety review, and requirements for documenting meeting discussions and outcome).

10. SUPPORTING DOCUMENTATION AND OPERATIONAL CONSIDERATIONS

10.1. Appendix 1: Regulatory, Ethical, and Study Oversight Considerations

10.1.1. Regulatory and Ethical Considerations

- This study will be conducted in accordance with the protocol and with the following:
 - Consensus ethical principles derived from international guidelines including the Declaration of Helsinki and Council for International Organizations of Medical Sciences (CIOMS) International Ethical Guidelines
 - Applicable ICH Good Clinical Practice (GCP) Guidelines
 - Applicable laws and regulations
- The protocol, protocol amendments, ICF, IB, and other relevant documents (eg, advertisements) must be submitted to an IRB/IEC by the Investigator and reviewed and approved by the IRB/IEC before the study is initiated.
- Any amendments to the protocol will require IRB/IEC approval before implementation of changes made to the study design, except for changes necessary to eliminate an immediate hazard to study participants.
- The Investigator will be responsible for the following:
 - Providing written summaries of the status of the study to the IRB/IEC annually or more frequently in accordance with the requirements, policies, and procedures established by the IRB/IEC
 - Notifying the IRB/IEC of SAEs or other significant safety findings as required by IRB/IEC procedures
 - Providing oversight of the conduct of the study at the site and adherence to requirements of 21 Code of Federal Regulations (CFR), ICH guidelines, the IRB/IEC, European regulation 536/2014 for clinical studies (if applicable), and all other applicable local regulations

10.1.2. Financial Disclosure

Investigators and Sub-Investigators will provide Alexion with sufficient, accurate financial information as requested to allow Alexion to submit complete and accurate financial certification or disclosure statements to the appropriate regulatory authorities. Investigators are responsible for providing information on financial interests during the course of the study and for 1 year after completion of the study.

10.1.3. Informed Consent Process

- It is the responsibility of the Investigator to obtain signed (written or electronic signature) informed consent from all study participants prior to any study-related procedures including screening assessments.
- The Investigator or his/her representative will explain the nature of the study (including but not limited to the objectives, potential benefits and risks, inconveniences, and the participant's rights and responsibilities) to the participant or his/her legally authorized representative, defined according to local and country regulations where the study is taking place, and answer all questions regarding the study.
- Participants must be informed that their participation is voluntary. Participants or their legally authorized representative will be required to sign a statement of informed consent or a certified translation if applicable, that meets the requirements of 21 CFR 50, local regulations, EU General Data Protection Regulation (GDPR), ICH guidelines, Health Insurance Portability and Accountability Act (HIPAA) requirements, where applicable, and the IRB/IEC or study center.
- The medical record must include a statement that signed (written or electronic) informed consent was obtained before the participant was screened in the study and the date the written consent was obtained. The authorized person obtaining the informed consent must also sign the informed consent form(s).
- Participants must be re-consented to the most current version of the informed consent form(s) during their participation in the study.
- A copy of the signed (written or electronic) informed consent documentation (ie, a complete set of participant information sheets and fully executed signature pages) must be provided to the participant or the participant's legally authorized representative, as applicable. This document may require translation into the local language. Signed (written or electronic) consent [or assent] forms must remain in each participant's study file and must be available for verification at any time.
- Participants who are rescreened are required to sign a new ICF (see Section 5.4).

